8.4.6 Management of GM-CSF (sargramostim) Adverse Reactions

- Hold GM-CSF if total white blood cell (WBC) count is $> 50 \times 10^9/L$ and/or absolute neutrophil count (ANC) $> 20 \times 10^9/L$; resume at 50% dose when the WBC count and/or ANC is $< 20 \times 10^9/L$. Administer full dose with subsequent cycles and modify again if the WBC count exceeds $50 \times 10^9/L$ and/or ANC exceeds $20 \times 10^9/L$
- Localized skin reactions to GM-CSF are common, and GM-CSF can be continued when reactions are mild. Rotation of sites of injections is recommended when skin reactions occur. Consider use of antihistamines. If \geq CTCAE Grade 3 injection site reactions occur, stop GM-CSF for the current cycle and discontinue GM-CSF for subsequent cycles of therapy
- Serious allergic reactions (including anaphylactic reactions) have been reported with GM-CSF. If \geq CTCAE Grade 3 allergic reaction occurs discontinue GM-CSF

8.4.7 Therapy and Procedures Allowed During Trial

Any treatment needed for patient wellbeing (including supportive care) that will not interfere with IMP administration may be given at the discretion of the Investigator.

Radiotherapy:

Radiotherapy may be administered for local control of primary site in patients who have achieved a response at metastatic sites but with residual primary tumor after 8 cycles. Furthermore, radiotherapy to localized painful lesions is allowed, provided at least one measurable/MIBG evaluable lesion is not irradiated.

Lesions irradiated during protocol therapy cannot be used to assess tumor response. Patients should be evaluated prior to radiotherapy with appropriate tumor imaging.

For discontinuation criteria due to PD, see Section 7.12.

Surgery:

Surgery to primary site is allowed for patients who have achieved a response at metastatic sites but with residual primary tumor after 8 cycles. If a patient is to undergo surgery due to residual primary tumor, a pause in treatment with IMPs will be allowed. This should be as short as possible with a delay of next cycle of maximum 3 weeks.

8.4.8 Prohibited Therapy/Procedures During the Trial

The following are prohibited during the trial:

- Systemic anti-cancer treatment, other than naxitamab and IT.
- St John's wort
- CYP3A4 enzyme-inducing anticonvulsants phenytoin, phenobarbital, carbamazepine
- Aprepitant as an anti-emetic
- Radiotherapy to metastatic site(s) other than mentioned in Section [8.4.7](#)
- Surgery to metastasis site(s) other than mentioned in Section [8.4.7](#)
- Any live-attenuated vaccines
- IV Immunoglobulin
- Any IMP not defined in this protocol

Except for IV methylprednisolone or equivalent corticosteroid for pre-medication prior to naxitamab infusion (see Section [8.4.1](#)), pharmacologic doses of systemic corticosteroids should be used ONLY for life-threatening conditions (i.e., life-threatening allergic reactions or anaphylaxis such as bronchospasm or stridor) unresponsive to other measures. The use of dexamethasone as an anti-emetic is not permitted. Corticosteroid therapy can be used as a premedication for transfusion in patients known to have a history of transfusion reactions or for treatment of an unexpected transfusion reaction (hydrocortisone 2 mg/kg or less or an equivalent dose of an alternative corticosteroid).

The use of corticosteroid during protocol therapy beyond pre-medication (as mentioned above) must be clear from the indication in the eCRF.

9 PROCEDURES AND ASSESSMENTS

9.1 Efficacy Assessments

9.1.1 Response Assessments

The primary endpoint is ORR. This will be based on BM biopsies and aspirates (histology, cytology) and imaging and assessed according to INRC³⁷ (see [Table 5](#), [Table 6](#), [Table 7](#) and [Table 8](#)). The imaging should be done either as:

- CT/MRI and ^{123}I -MIBG + single-photon emission computed tomography (SPECT)/CT **or**
- CT/MRI and ^{123}I -MIBG whole body planar scan if no hybrid gamma camera is available **or**
- CT/MRI and FDG-PET/CT if MIBG-nonavid tumor

The same imaging modality should preferably be used throughout the trial (please refer to the imaging acquisition guideline).

BM examinations should comprise bilateral BM trephine biopsies and BM aspirates (i.e., 2+2 samples) as per INRC⁴³ (please refer to laboratory manual).

BM trephine biopsies should be evaluated by histology and immunohistochemistry (IHC). Two highly specific target antigens should be used for IHC, such as synaptophysin, tyrosine hydroxylase, chromogranin A, or paired-like homeobox 2b (PHOX2B). The target antigens used for IHC should remain the same throughout the trial. BM aspirates should be evaluated by cytology and MRD (please see [Section 9.1.1.1](#)). If volume of aspirates is not sufficient, BM response assessment should be prioritized over MRD assessment by RTqPCR.

Images and BM biopsies/aspirates (excluding results from RTqPCR, see [Section 9.1.1.1](#)) will be assessed locally at site but will also be reviewed centrally by independent external experts. The local response assessment will be used throughout the trial for the decision to continue or discontinue IMPs. Imaging and BM biopsies/aspirates must be done within 7 days (+ 3 days) of the same response assessment (except at screening). The centralized review will be done retrospectively.

Table 5 Primary (soft tissue) Tumor response

Response	Anatomic + MIBG (FDG-PET [†]) Imaging	
CR	< 10 mm residual soft tissue at primary site AND Complete resolution of MIBG or FDG-PET uptake (for MIBG-nonavid tumors) at primary site	
PR	$\geq 30\%$ decrease in longest diameter of primary site AND MIBG or FDG-PET uptake at primary site stable, improved, or resolved	
PD	$> 20\%$ increase in longest diameter taking as reference the smallest sum on study (this includes the baseline sum if that is the smallest on study) AND Minimum absolute increase of 5 mm in longest dimension [‡]	
SD	Neither sufficient shrinkage for PR nor sufficient increase for PD at the primary site	
Abbreviations:	CR, complete response CT, computed tomography FDG, $[18\text{F}]$ fluorodeoxyglucose MIBG, metaiodobenzylguanidine	PD, progressive disease PET, positron emission tomography PR, partial response

Response	Anatomic + MIBG (FDG-PET [†]) Imaging
	SD, stable disease
*Not for use in assessment of metastatic sites.	
[†] Used for MIBG-nonavid tumors.	
[‡] Mass that does not meet PD measurement criteria but has fluctuating MIBG avidity will not be considered PD.	

Table 6 Tumor response at metastatic soft tissue and bone sites

Response	Anatomic + MIBG (FDG-PET [*]) Imaging
CR	Resolution of all sites of disease, defined as: 
 Nonprimary target and nontarget lesions measure < 10 mm AND Lymph nodes identified as target lesions decrease to a short axis < 10 mm AND MIBG uptake or FDG-PET uptake (for MIBG-nonavid tumors) of nonprimary lesions resolves completely
PR	
 ≥ 30% decrease in sum of diameters[†] of nonprimary target lesions compared with baseline AND all of the following: 
 Nontarget lesions may be stable or smaller in size AND No new lesions AND ≥ 50% reduction in MIBG absolute bone score (relative MIBG bone score ≥ 0.1 to ≤ 0.5) OR ≥ 50% reduction in number of FDG-PET-avid bone lesions[‡]
PD	Any of the following: 
 Any new soft tissue lesion detected by CT/MRI that is also MIBG avid or FDG-PET avid Any new soft tissue lesion seen on anatomic imaging that is biopsied and confirmed to be NB or ganglioneuroblastoma Any new bone site that is MIBG avid A new bone site that is FDG-PET avid (for MIBG-nonavid tumors) AND has CT/MRI findings consistent with tumor OR has been confirmed histologically to be NB or ganglioneuroblastoma >20% increase in longest diameter taking as reference the smallest sum on study (this includes the baseline sum if that is the smallest on study) AND minimum absolute increase of 5mm in sum of diameters of target soft tissue lesions Relative MIBG score ≥ 1.2[§]
SD	Neither sufficient shrinkage for PR nor sufficient increase for PD of nonprimary lesions
Abbreviations:	
CR, complete response CT, computed tomography FDG, [18F] fluorodeoxyglucose MIBG, metaiodobenzylguanidine MRI, magnetic resonance imaging
 
PD, progressive disease PET, positron emission tomography PR, partial response SD, stable disease

* Used for MIBG-nonavid tumors
†Sum of diameters is defined as the sum of the short axis of discrete lymph nodes (ie, cervical, axillary nodes) added to the sum of the longest diameters of non-lymph node soft tissue metastases. Masses of conglomerate nondiscrete lymph nodes will be measured using longest diameter.
§ Relative MIBG score (based on Curie) is the absolute score for bone lesions at time of response assessment divided by the absolute score for bone lesions at baseline before therapeutic interventions
‡For patients with soft tissue metastatic disease, resolution of MIBG and/or FDG-PET uptake at the soft tissue sites is not required; all size reduction criteria must be fulfilled.

Table 7 BM metastasis response

Response	Cytology/Histology
CR	BM with no tumor infiltration on reassessment, independent of baseline tumor involvement
PD	Any of the following: -BM without tumor infiltration that becomes > 5% tumor infiltration on reassessment or

	-BM with tumor infiltration that increases by > twofold and has >20% tumor infiltration on reassessment
MD	Any of the following: -BM with $\leq 5\%$ tumor infiltration and remains >0 to $\leq 5\%$ tumor infiltration on reassessment or -BM with no tumor infiltration that has $\leq 5\%$ tumor infiltration on reassessment or -BM with $>20\%$ tumor infiltration that has >0 to $\leq 5\%$ tumor infiltration on reassessment
SD	BM with tumor infiltration that remains positive with $>5\%$ tumor infiltration on reassessment but does not meet CR, MD, or PD criteria
NOTE. In the case of discrepant results between aspirations or core biopsies from two or more sites taken at the same time, the highest infiltration result should be reported using the criteria in this table	
Abbreviations:	BM, bone marrow PD, progressive disease CR, complete SD, stable disease response MD, minimal disease

Overall response

Overall response will be defined by combining response of the individual components (i.e., primary (soft tissue) tumor, metastatic soft tissue, bone sites, and BM metastasis).

Table 8 Determination of overall response

Response	Criterion
CR	All components meet criteria for CR
PR	PR in at least one component and all other components are either CR, MD* (BM), PR (bone), or NI†; no component with PD
MR	PR or CR in at least one component but at least one other component with SD; no component with PD
SD	SD in one component with no better than SD or NI† in any other component; no component with PD
PD	Any component with PD
Abbreviations:	BM, bone marrow NI, not involved CR, complete response PD, progressive disease MD, minimal disease PR, partial response MR, minor response SD, stable disease (a minimum duration of 6 weeks is required [#]) ⁴⁴

* For BM assessment only.
† Site not involved at trial entry and remains uninvolved.
Time window of – 5 days is acceptable

9.1.1.1 Response assessment of BM MRD⁴³:

BM aspirate samples for RTqPCR should be taken at baseline, after C2 and after C4. RTq-PCR analyses will be performed centrally.

The results of RTqPCR will be reported as the cycle threshold (Ct) value in which the expression of the NB mRNA for tyrosine hydroxylase and PHOX2B is normalized to the internal control (the reference housekeeping gene; β 2-microglobulin)⁴³. The lower Ct for reporting RTqPCR for the neuroblastoma mRNAs is a Ct value of 40. A tumor negative BM has a Ct value ≥ 40 for all of the neuroblastoma mRNAs examined, when amplification of the reference housekeeping gene generates a Ct value of <25 . Further details on BM sampling for RTqPCR analysis will be provided in the laboratory manual.

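### Table 6 gives two incompatible limits for a partial response in bone, so an MIBG-avid patient with more than 90% but incomplete clearance has no consistent response category

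*Combined protocol and SAP*

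**What the plan says.** The primary endpoint (section 6.1) is the proportion of patients with a centrally assessed CR or PR by INRC at or before the end of four cycles. Section 9.1.2 places the relevant assessments after cycles 2 and 4.

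Table 6 in section 9.1.1 covers metastatic soft tissue and bone:

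- **PR**, MIBG part: "≥ 50% reduction in MIBG absolute bone score (relative MIBG bone score ≥ 0.1 to ≤ 0.5". The alternative based on FDG-PET lesion counts falls under the table note "Used for MIBG-nonavid tumors".
- **CR**, uptake part: "MIBG uptake or FDG-PET uptake (for MIBG-nonavid tumors) of nonprimary lesions resolves completely".
- **SD**: "Neither sufficient shrinkage for PR nor sufficient increase for PD of nonprimary lesions".
- **PD**, score part: a relative MIBG score of 1.2 or more.
- **Definition** in the table notes: "Relative MIBG score (based on Curie) is the absolute score for bone lesions at time of response assessment divided by the absolute score" at baseline.

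Table 8 combines the components. Overall PR requires "PR in at least one component and all other components are either CR, MD* (BM), PR (bone), or NI†; no component with PD". Overall MR is "PR or CR in at least one component but at least one other component with SD; no component with PD". Section 12.4 counts not-evaluable patients as non-responders.

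The same tables serve local and central readers. Under section 9.1.1, local reads guide decisions on continuing IMP and central review is retrospective. Under section 12.4, the local evaluation is the sensitivity analysis.

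**The concern.** The two halves of the PR criterion do not describe the same set of patients. A reduction of at least 50% means a relative score of 0.5 or less, with no lower limit. The bracket adds a lower limit of 0.1. A patient whose bone score falls by more than 90% but not to zero satisfies the first half and fails the second.

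Two consequences follow for the primary endpoint. First, under the bracket a patient with a 95% reduction scores worse than one with a 50% reduction. Second, a reader who follows the lead words and one who follows the bracket give different answers for the same scan. Central and local results could then disagree for a reason unrelated to the images, and the sensitivity analysis could not separate that from genuine reader disagreement.

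**Working it through.** **1. Where a relative score r with 0 < r < 0.1 goes (MIBG-avid bone disease, other PR conditions met)**

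| Row | Condition | Met? |
|---|---|---|
| CR | uptake fully resolved | No, because r > 0 |
| PR, lead words | reduction ≥ 50%, i.e. r ≤ 0.5 | Yes |
| PR, bracket | 0.1 ≤ r ≤ 0.5 | No |
| PR, FDG route | MIBG-nonavid tumors only | Not available |
| PD, score | r ≥ 1.2 | No |
| SD | too little shrinkage for PR and too little growth for PD | Poor fit: shrinkage exceeds 90% |

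**2. Effect through Table 8 if the bracket binds.** If bone is called SD, overall PR is blocked and the result is MR (another component at CR or PR) or SD. If the assessment is called NE, section 12.4 makes it a non-response. Neither label gives a CR or PR at that assessment.

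**3. Worked case, baseline bone score 20**

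- residual 10: r = 10/20 = 0.50, PR
- residual 2: r = 2/20 = 0.10, PR
- residual 1: r = 1/20 = 0.05, PR by the lead words, not PR by the bracket

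**4. Who can reach the gap (assuming whole-number scores).** The condition is residual/baseline < 0.1 with residual ≥ 1.

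- 1/10 = 0.100 is still PR and 1/11 = 0.091 is in the gap, so the baseline must be at least 11.
- 2/20 = 0.100 is still PR and 2/21 = 0.095 is in the gap, so a residual of 2 needs a baseline of at least 21.

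The only entry threshold stated is a Curie score of at least 3, for refractory patients (section 7.11.1). The documents give no distribution of baseline scores.

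**5. Across the two assessments.** PR after cycle 2 followed by a gap score after cycle 4 is still a responder. So is a gap score after cycle 2 followed by overall CR after cycle 4. The patient is lost only when neither assessment yields CR or PR.

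**6. The plan's own design figure.** Inputs from sections 12.2 and 12.4.1: null 20%, alternative 40%, two-sided exact binomial test at 5%, 41 evaluable patients. (The figures reproduce with 20% as the null, as in the text; the two rate headings in Table 11 appear swapped.)

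- Rejection above the null: at least 14 of 41. Upper-tail error 0.0242; power P(X ≥ 14 | 41, 0.40) = 0.822, against the stated 82%.
- 41/0.8 = 51.25, rounded up to 52, as stated.

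**7. Weight of one patient**

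| n | One patient | Rejects | Does not reject |
|---|---|---|---|
| 52 | 1/52 = 1.9 points | 17/52, p = 0.035 | 16/52, p = 0.057 |
| 41 | 1/41 = 2.4 points | 14/41, p = 0.031 | 13/41, p = 0.076 |

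**8. Illustration only.** Let g be the assumed share of true responders lost to the gap. ORR becomes 0.40 × (1 − g), and power is P(X ≥ 14 | 41, ORR).

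| g | ORR | Power |
|---|---|---|
| 0 | 40% | 82.2% |
| 2.5% | 39% | 78.6% |
| 5% | 38% | 74.6% |
| 10% | 36% | 65.4% |

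**The case against.** A sensible reader would take the 50% reduction as the operative rule and the bracket as a loose gloss, so that a score of 0.05 is simply PR. That is plausible, but no section says so, and the bracket is stated as a numerical range.

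A reader might infer the opposite: that such a patient necessarily falls to SD and is a non-responder in the primary ORR. The documents do not support that either. The SD row is defined by insufficient shrinkage, not as a residual category, and it fits a reduction above 90% poorly. Non-response is also not automatic, because a PR after cycle 2 or a CR after cycle 4 still counts.

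The bracket may come from the INRC, which section 9.1.1 says the tables follow. The source is not available here, so this cannot be checked. If the limit is inherited, changing it departs from the criteria named in the endpoint. That is a reason to check first and document the choice. It does not remove the conflict within the protocol's own row.

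Finally, few patients may be affected. This stands: reach is confined to high baseline scores, and any percentage put on it is an assumption.

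**Conclusion.** The Table 6 PR row is internally inconsistent, and it leaves relative MIBG bone scores above 0 and below 0.1 without a consistent category. Read literally, the bracket makes the assessment a non-response and ranks a deeper response below a shallower one in the primary endpoint.

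The number of patients is probably small and cannot be estimated from the documents. The reach stated here rests on whole-number scoring. The analysis denominator may lie below 52, since the FAS drops patients without centrally confirmed evaluable disease (section 12.3), so both 52 and 41 are shown. At either size, one reclassified patient at the boundary changes the conclusion of the test. The power figures show sensitivity to an assumed loss; they are not forecasts. The correction is worth making because it touches the primary endpoint and costs little if made before central reads.

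**What to change.** Before central review starts:

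1. Check the bracket against the cited INRC.
2. Reconcile it with the row's lead criterion, for example as: relative MIBG bone score ≤ 0.5, not meeting CR. Any reduction of at least 50% short of CR is then PR. A lower bound of merely > 0 would leave a hole: if Table 6 is scored as one component, a patient with fully cleared bone (score 0) and soft-tissue metastases at PR would be neither CR nor PR.
3. Use the same wording in the central-review charter and for local reads.
4. If the 0.1 floor is kept because the cited criteria contain it, state the category for scores below 0.1 and add a sensitivity ORR that counts them as PR.

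The cost is a one-line change to Table 6 and matching text in the charter, with no new data; item 4 would add one supplementary analysis. The downside is a possible small, documented departure from the literal cited criteria.

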6.2 Secondary Endpoints

1. ORR after 2 cycles defined as the proportion of patients obtaining a centrally assessed CR or PR according to the INRC at completion of two treatment cycles
2. Duration of response (DoR), defined as the time from first centrally assessed OR (CR or PR according to the INRC) to PD or death
3. CR rate, defined as the proportion of patients obtaining a centrally assessed CR according to the INRC at or before completion of four treatment cycles
4. CR rate after two cycles defined as the proportion of patients obtaining a centrally assessed CR according to the INRC at completion of two treatment cycles
5. Minor response (MR) rate, defined as the proportion of patients obtaining a centrally assessed MR according to the INRC at or before completion of four treatment cycles
6. "MR or better" rate, defined as the proportion of patients obtaining a centrally assessed CR, PR or MR according to the INRC at or before completion of four treatment cycles
7. Proportion of patients with disease in BM at enrollment who obtain centrally assessed CR in BM and convert to minimal residual disease (MRD) negative (assessed by reverse transcriptase-quantitative polymerase chain reaction (RTqPCR)) at or before completion of four cycles
8. Time to First Subsequent Therapy or death (defined as the time from initiation of treatment with investigational medicinal products (IMP) until death or start of new anti-cancer treatment (prohibited as per protocol))
9. PFS defined as the time from first IMP administration until centrally assessed PD or death, whichever comes first
10. OS defined as the time from first IMP administration until death
11. 1- and 2-years PFS defined as the proportion of patients alive and with no centrally assessed PD at 1- and 2 year, respectively after first IMP administration
12. 1- and 2-year OS defined as the proportion of patients alive at 1- and 2 years after first IMP administration
13. Safety incl. incidence of AEs and SAEs graded according to Common Terminology Criteria for AEs (CTCAE) version 5.0
14. Pain during naxitamab infusions as assessed by Wong Baker- and FLACC scales
15. Incidence of ADA (including assessment for neutralizing potential and time to first positive ADA assessment from first day of naxitamab administration)
16. Number of naxitamab infusions done in an out-patient setting defined as infusions not requiring admission to hospital due to adverse events

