12.11 Subgroup Analyses

The primary endpoint will be analyzed and presented for the following subgroups:

- primary refractory vs. first relapse vs first PD during frontline therapy
- soft tissue lesions present at baseline (yes / no)
- tumor MYCN amplification status (yes / no)
- prior exposure to anti-GD2 antibody therapy (yes / no)
- ADA status (negative at all times / positive at any time)
- disease compartment (bone, BM, bone and BM combined (*i.e.*, OR excl. soft tissue lesions) as well soft tissue)
- geographical region

- site
- age group (0 - <2, 2 - <6, 6 - <12, 12 - <18 and >=18 years)
- body weight group (<20 kg; 20-<50 kg; >=50 kg)
- sex (male/female)
- race

Overviews of AEs will be presented for the following subgroups:

- primary refractory vs. first relapse vs first PD during frontline therapy
- ADA status (negative at all times / positive at any time)
- geographical region
- age group (0 - <2, 2 - <6, 6 - <12, 12 - <18 and >=18 years)
- body weight group (<20 kg; 20-<50 kg; >=50 kg)
- sex (male/female)
- race

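### Tables 7 and 8 give never-involved marrow two different labels (CR and NI), so a patient with only stable disease can count as MR in secondary endpoints 5 and 6

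*Combined protocol and SAP*

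**What the plan says.** Section 9.1.1 builds overall response from component responses: primary tumor (Table 5), metastatic soft tissue and bone (Table 6) and marrow (Table 7). Table 8 combines them.

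- **Table 7, CR row:** marrow is CR if it is "BM with no tumor infiltration on reassessment, independent of baseline tumor involvement". The table also covers patients who enter with clear marrow. One PD criterion, for example, is "BM without tumor infiltration that becomes > 5% tumor infiltration on reassessment".
- **Table 8, NI footnote:** "Site not involved at trial entry and remains uninvolved".
- **Table 8, MR row:** "PR or CR in at least one component but at least one other component with SD; no component with PD".
- **Table 8, SD row:** SD in one component with "no better than SD or NI† in any other component; no component with PD".
- **Table 8, PR row:** accepts both CR and NI in the remaining components.
- **Table 8, CR row:** requires CR in every component and does not mention NI.

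Section 6.2 makes the MR rate and the MR-or-better rate, both centrally assessed by the end of four cycles, secondary endpoints 5 and 6. Section 12.4.2 presents them like the primary endpoint, with exact 95% confidence intervals. Section 6.3 repeats them on local assessments. Section 12.11 also presents the primary endpoint by "disease compartment (bone, BM, bone and BM combined" and soft tissue.

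**The concern.** A marrow that was clear at entry and is still clear fits the Table 7 definition of CR and the Table 8 definition of NI. The protocol prints no order of precedence, and the choice can change the overall category of a patient whose disease has not changed.

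The situation will arise. Under inclusion criterion 5 a single MIBG-positive site is enough, so marrow disease is not required. Exclusion criterion 8 removes marrow-only disease, so every patient has a non-marrow component that can be SD.

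Two secondary endpoints are at stake. If Table 7 is applied as written, endpoints 5 and 6 count stable patients as having a minor response. If central and local readers adopt different conventions, their results will differ for a reason unrelated to the images or the marrow samples.

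**Working it through.** **1. Does the label change the category?** The plan states no figure for the MR endpoints, so the check is on the rules. Take marrow clear at entry and at reassessment. Give the two other tabulated components (Table 5; Table 6) every ordered combination of CR, PR, SD, PD and NI except NI with NI, which leaves 24. Score each by Table 8, once with marrow = CR and once with marrow = NI.

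| Other components | Marrow = CR | Marrow = NI |
|---|---|---|
| SD, SD | MR | SD |
| SD, NI (either order) | MR | SD |
| CR, CR | CR | fits no row |
| the other 20 combinations | same result | same result |

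Three of the 24 move between SD and MR. None moves from SD to PR or CR, and every PR result is the same under both labels. The CR, CR line shows a second defect: giving NI precedence without touching the CR row leaves a patient with complete response at both other components without a category. Among the 20 unchanged combinations, CR with NI (either order) fits no row under either label, again because the CR row does not accept NI.

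**2. Illustration of size.** Inputs:

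- *SD share*, from the studies cited in section 4.3.4: 22/53 = 41.5% (IT + dinutuximab + GM-CSF, enlarged cohort); 13/46 = 28.3% (first naxitamab + IT series); 10/44 = 22.7% (second series). The second series reports ten SD among 36 evaluable patients. All 44 are used here because section 12.4 keeps non-evaluable patients in the denominator.
- *Share with marrow uninvolved at entry*: not given anywhere. Assumed 30–70%, independent of response.
- *Number of patients*: Table 11 has 41 before drop-out, and 41/(1 − 0.20) = 51.25, rounded up to 52, which reproduces the plan's figure. The 20% allowance covers patients without centrally evaluable disease or without a post-baseline assessment. Neither group can supply a centrally assessed SD, so 41 is the relevant count.

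Formula: points moved = SD share × uninvolved-marrow share; patients moved = 41 × that product.

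| SD share | 30% uninvolved | 70% uninvolved |
|---|---|---|
| 22.7% | 6.8 points (2.8 patients) | 15.9 points (6.5) |
| 28.3% | 8.5 points (3.5) | 19.8 points (8.1) |
| 41.5% | 12.5 points (5.1) | 29.1 points (11.9) |

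The range is about 7–29 points, or about 3–12 of 41 patients. Using 10/36 = 27.8% in place of 10/44 gives 0.278 × 0.30 × 41 = 3.4 patients at the low end, still about 3.

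**The case against.** The best reply is that NI already prevails. Table 8 sets the overall category, its NI definition is specific, and NI would never apply to marrow if Table 7 always overrode it. The Table 7 rows that start from clear marrow concern marrow that later turns positive, which NI excludes by definition. A careful reader can therefore reach SD. That reading is available, but it is not printed, and on its own it leaves the complete-response patient in step 1 without a row. To classify that patient as CR, a reader is pushed to code clear marrow as CR, and the same convention turns SD into MR elsewhere.

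Several limiting points stand:

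- Endpoints 5 and 6 are not among the synopsis's key secondary endpoints, and the secondary response endpoints are descriptive.
- The response categories are tabulated separately, so MR can be seen apart from CR and PR.
- Section 7.2.1 gives MR and SD the same option after 8 cycles, so the label does not change that step.
- Secondary endpoint 7 is restricted to patients with marrow disease at enrollment and is unaffected.
- The INRC publication, the laboratory manual or the imaging charter may contain a precedence rule. They were not available for this review.

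A reader might infer that a primary resected before entry raises the same problem under Table 5. The text does not clearly support this. Table 5 requires uptake at the primary site to resolve completely, which suggests that uptake was there before, and it has no counterpart to Table 7's disregard of baseline status.

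**Conclusion.** The two tables conflict as printed, and the conflict changes a reported result. With never-involved marrow and SD at every other involved site, the patient is MR under Table 7's label and SD under Table 8's. Endpoints 5 and 6 can therefore include patients in whom nothing improved.

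The size is illustrative only: about 7–29 percentage points, or about 3–12 of 41 evaluable patients. It rests on the assumed 30–70% share, on independence between marrow status and response, on SD shares from other studies (both naxitamab series were assessed after two cycles, while endpoints 5 and 6 run to four), and on every affected patient being coded CR in marrow. The contradiction itself does not depend on these numbers.

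Two stronger readings are not supported:

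- *That the primary ORR is inflated.* No combination moves from SD to PR or CR.
- *That section 12.11 does count never-involved marrow as a marrow response.* The section does not say whether patients without disease in a compartment are included. It could have the same problem if the presentation is not limited to patients with that compartment involved at baseline.

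**What to change.** 1. Add one sentence under Table 8: for overall response, any component, marrow included, that was uninvolved at entry and is still uninvolved is scored NI and cannot supply the PR or CR required by the MR row.
2. Change the Table 8 CR row so that all involved components must meet CR and all others are NI. This has to accompany item 1, otherwise some complete responders have no category.
3. Leave Table 7's wording as it is. The endpoints are defined by the INRC, and the precedence sentence resolves the conflict without redefining marrow CR.
4. In section 12.11, limit each compartment result to patients with that compartment involved at baseline.
5. Apply the same rule to the central review before reads begin, and to the local assessments. Central review is retrospective, so the convention can be fixed in advance.

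The cost is a few lines of text in the protocol and the central-review instructions, with no new data. The downside is that the reported MR and MR-or-better rates may be lower.
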